**\*\*\* Drugs, Reagents, Chemicals, or Biologic Products \*\*\***

**6. Drugs, Reagents, Chemicals, Biologic Products, or Dietary Supplements, Vitamins, and Other Food Agents**

Pilot	Phase I	Phase II
Phase III	Phase IV	X Not Phased

List placebo if it is considered a drug (contains more than inactive ingredients). For example, normal saline is considered a drug that should be listed, whereas placebo tablets are usually inert ingredients that do not need to be listed.

- b) Please list in the space below all investigational drugs, reagents or chemicals to be administered to subjects during this study. Attach all applicable Investigator Brochures in section #16 (Attachments).
- c) Please list in the space below all FDA approved drugs, reagents, chemicals to be administered to subjects during this study. Attach all applicable package inserts in section #16 (Attachments).
- d) Please list in the space below all dietary supplements, vitamins, minerals, or foods to be administered to subjects during this study.

Please read the IND Statements.

---

**\*\*\* Other Levels Of Review \*\*\***

**7. Other Levels Of Review**

**1. University Radiation Safety**

Protocols that involve non-standard of care radioactive materials (which includes the terms "radioisotopes", "radionuclides", "radiopharmaceuticals", and "nuclear medicine studies", e.g., "PET", "MUGA", "Zevalin", and/or specific radionuclides such as "F-18", "Tc-99m", "Th-201", "I-131", "Ra-223", "Y-90", etc.) will receive review by the Radiation Safety Officer (RSO) and/or Radiation Safety Committee (RSC). For information on how to submit for radiation safety review, see RSC instructions or contact the Radiation Safety Officer at [name].

- X **Not Applicable**  
Yes, study involves radioactive materials (per instructions, submit to RSC before IRB)

**Protocol Title:** Analysis of hemostatic agents compared to physiologic hemostasis

---

## 2. Institutional Biosafety

Experiments involving the deliberate transfer of Recombinant or Synthetic Nucleic Acid Molecules (e.g., Gene Transfer), or DNA or RNA derived from Recombinant or Synthetic Nucleic Acid Molecules, or Microorganisms containing Recombinant or Synthetic Nucleic Acid Molecules and/or infectious agents (including select agents and toxins as defined by CDC and/or Animal and Plant Health Inspection Service (APHIS)) into one or more human research participants must be reviewed by the SLU Biological Safety Officer. Most of these protocols also require review and approval by the SLU Institutional Biosafety Committee (IBC). Please contact the SLU Biological Safety Officer at [name] for more information.

- Not Applicable**  
**Yes, study requires Institutional Biosafety review**

## 3. Pharmacy, Therapeutics, Nutrition, and Transfusion (PTNT) Committee

Saint Louis University Hospital requires that all research involving the administration of medications within the hospital (including outpatient areas such as the Emergency Department, Outpatient Center, Saint Louis University Hospital-South Campus, etc.) be reviewed and approved by the Pharmacy, Therapeutics, Nutrition, and Transfusion (PTNT) Committee and that study drugs are received, stored, prepared, and dispensed by the Hospital's Department of Pharmacy Services. Please contact the Investigational Drug Services Clinical Pharmacist at [name] or [contact] for more information.

- Not Applicable**  
**Yes, study requires PTNT review**

## 4. Saint Louis University Hospital

All research involving Saint Louis University Hospital, including the Emergency Department, inpatient or outpatient services (including outpatient surgery at ABI and the infusion center at DOB) and medical record access, requires approval from the Saint Louis University Hospital Research Review Committee prior to study initiation. This process is designed to facilitate compliance with state and federal regulations as they pertain to research in hospitals and clinical research billing. Documents should be submitted as soon as possible, or at the latest, concurrently with IRB submission. Please contact the Research Compliance Office at [name] or [contact] of the SLU Clinical Trials Office (CTO) at [name] or [contact] for more information.

- Not Applicable**  
 **Yes, study requires Saint Louis University Hospital review**

## 5. SSMSL

All research involving SSMSL locations (including Cardinal Glennon), including inpatient or outpatient services and medical record access, requires approval from the SSM STL or SSM Cardinal Glennon Research Business Review (RBR) prior to study initiation. This process is designed to facilitate

**Protocol Title:** Analysis of hemostatic agents compared to physiologic hemostasis

---

compliance with state and federal regulations as they pertain to research in hospitals and clinical research billing. While researchers can begin to complete the SSM RBR form at any time, the form should not be submitted until the IRB and the CTO have approved the study. Please contact the SSMSL Office at [name] or [contact] for more information.

- X **Not Applicable**  
Yes, study requires RBR review

6. Does this project require registration on ClinicalTrials.gov, and/or is this project subject to the NIH GCP Training Requirement? (Select "Yes" if either apply) Y

Registration may be required if any of the following apply: 1) The project meets the FDAAA definition of an "Applicable Clinical Trial", which requires registration on ClinicalTrials.gov. 2) As of January 1, 2017, a new NIH policy mandated biomedical and behavioral "Clinical Trials" to be registered on ClinicalTrials.gov. In addition, NIH policies require personnel on NIH "Clinical Trials" to take GCP training every three years. 3) Registering may be required for Journal Publication (ICMJE). Please review relevant definitions here. Contact the CTO at [contact] with questions about registering on ClinicalTrials.gov and refer to the training page of the IRB website for information on NIH GCP Training requirements.

---

\*\*\* Subject Population \*\*\*

8. Subject Population - In the space below, please detail the participants that you are requesting to recruit (include description of each group requested)

a) Expected age range of subjects. (For example ≥ 18 yrs to 90 yrs).

≥18 yrs to 75 years

b) Number of evaluable subjects to be accrued at SLU or SLU site (this includes all sites under the direction of the SLU PI). 144

Exceeding the number listed here is a protocol violation. Prior IRB approval is required if additional participants are to be accrued. If applicable, this number should be consistent with your power analysis described in 3d.

c) Number of evaluable subjects to be accrued study wide. \*?HELP?\* 144

d) If including vulnerable populations (minors, pregnant women and fetuses, neonates, non-English speaking, economically or educationally disadvantaged, prisoners, prisoners, adults temporarily or permanently unable to consent for themselves): 1) provide the rationale for the importance of including this population in the research, and 2) specify the measures being taken to minimize risks to potentially vulnerable subjects. Click on hyperlinks to access SLU Guidelines containing additional considerations and strategies for mitigating risks.

N/A

- e) If women, minorities, or minors are not included, a clear compelling rationale must be provided unless not applicable. Examples for not including minors: disease does not occur in children; drug or device would interfere with normal growth and development; etc. If federally funded reference appropriate section of the sponsors protocol/grant. **\*?HELP?\***

Children are not included because the study is being done from an adult clinic.

- f) If any specifically targeted subjects are students, employees, or laboratory personnel, specify the measures being taken to minimize the risks and the chance of harm to these potentially vulnerable subjects. See SLU Guidelines for additional considerations and strategies for mitigating risks.

- g) Describe how potential subjects will be identified for recruitment (e.g., chart review, referral from individual's treating physician, those individuals answering an ad). How will potential participants learn about the research, and how will they be recruited (e.g., flyer, e-mail, web posting, telephone, etc.)? Upload recruitment materials in the Attachment Section (#16). Important to remember: potential subjects cannot be contacted before IRB approval. NOTE: The use of SLU owned websites in an approved SLU format (e.g., Cancer Center website, etc.) are always approved methods of recruitment.

- a.) The patients selected for this study will be recruited and treated by physicians, [name] and [name], at the Saint Louis University Hospital and Saint Louis University UMG Practice Locations (St. Louis, MO).  
b.) Potential subjects will be recruited in person by the physician during regular appointments.  
c.) Study information may be posted to a SLU approved website in a standard approved format.

---

**\*\*\* Subject Population \*\*\***

**8. Subject Population (continued)**

Page numbers from a sponsor's protocol/grant may be referenced in 8h.

- h) **Inclusion and Exclusion Criteria.**

**Identify inclusion criteria.**

Inclusion criteria: ≥18 to <75 years of age with bilateral chronic or recurrent rhino sinusitis recalcitrant to medical therapy that requires ESS. Sinuses should have a similar degree of disease involvement bilaterally.

**Identify exclusion criteria.**

**Protocol Title:** Analysis of hemostatic agents compared to physiologic hemostasis

---

**Exclusion criteria:**

- (1) massive sinonasal polyposis,
- (2) history of underlying immunologic diseases, AIDS, cystic fibrosis, immunoglobulin deficiency, immotile cilia syndrome, and neutropenia,
- (3) known hypersensitivity to the aforementioned agents,
- (4) women who are pregnant or breastfeeding,
- (5) anyone with a known allergy to any of the treatments (potato starch, iodine, shellfish)
- (6) anyone with a known coagulopathy

- i) **Compensation. Explain the amount and schedule of compensation, if any, that will be paid for participation in the study. Include provisions for prorating payment.**

No monetary compensation was offered to either the participants in this study or the investigators, physicians or other health care providers for identifying and enrolling subjects.

- j) **Describe who will cover study related costs. Explain any costs that will be charged to the subject.**

All procedures are standard of care; no additional research-related costs will be incurred. Insurance will be billed for the standard of care procedure. The study hemostatic agents are part of the total cost for the operation. There is no difference in the cost of a procedure that uses hemostatic agents and one that does not use hemostatic agents.

- k) **Estimate the probable duration of the entire study including data analysis and publication. This estimate should include the total time each subject is to be involved and the duration the data about the subject is to be collected. If the study is Investigator-initiated, a timeline for individual subject recruitment, follow-up, total time for subject accrual, and data analysis for the study is required.**

Each patient's participation is expected to be about six weeks. Study should be complete by 3/31/2018.

Patients will be recruited and added to the study as they are seen in clinic. Each subject's participation is expected to be six weeks total. Evaluation at six weeks post operation is standard of care for Endoscopic Sinus Surgery. Subject accrual should take no longer than one year to achieve the goal of 144 patients. Data analysis will take up to 3 months.

---

**\*\*\* Risks \*\*\***

**9. Risks**

There is no research that can be considered totally risk free (e.g., a potential risk of breach of confidentiality). Therefore, when describing the risk, the lowest level of risk is "no more than minimal risk".

**Page numbers from a sponsor's protocol/grant may be referenced in 9.1, 9.2, 9.3, and 9.4.**

1. **Use of investigational devices. Please include the clinical adverse events (AEs) associated with each of the devices with an indication of frequency, severity and reversibility. This information can often be found in the Investigator(s) brochure. NOTE: Include any likely adverse effects associated with procedures that subjects may experience while in the study.**

**Protocol Title:** Analysis of hemostatic agents compared to physiologic hemostasis

---

2. **Use of investigational drugs. Please include the clinical AEs associated with each of the drugs with an indication of frequency, severity and reversibility. This information can often be found in the Investigator(s) brochure. NOTE: Include any likely adverse effects associated with placebos or washout periods that subjects may experience while in the study.**
  
3. **Use of FDA approved drugs, reagents, chemicals, or biologic products. Please include the clinical AEs associated with each of the drugs with an indication of frequency, severity and reversibility. This information can often be found in the package insert provided by the manufacturer. NOTE: Include any likely adverse effects associated with placebos or washout periods that subjects may experience while in the study.**
  
4. **Use of FDA approved devices. Please include the clinical adverse events (AEs) associated with each of the devices with an indication of frequency, severity and reversibility. This information can often be found in the Investigator(s) brochure. NOTE: Include any likely adverse effects associated with procedures that subjects may experience while in the study.**

a.) The risks of this study are minimal and non-life threatening. There are certain risks and discomforts that may be associated with this research. They include:

- 1) Allergic-type Adverse Reaction  
There is a rare possibility of an allergic-type adverse reaction to Arista™, Nexfoam™, Sinufoam™ Nasopore™, Nexfoam™ and Posisept™ and PosiseptX™. Patients may experience itching, hives, hay fever symptoms, wheezing, difficulty breathing, and/or new swelling. These reactions may be serious or life threatening. These are the same risks they would have if they did not participate in the study.
- 2) Bleeding.
- 3) Obstruction/Blockage of sinus passage. Post operative irrigations will remove any excess material. Also, debridement during post operative visits will remove any material that irrigation can't.
- 4) Pain
- 5) Infection-- [name] and [name] will evaluate patients for signs of infection during post operative visits.
- 6) Delayed/ Asymmetric healing. One nostril will receive therapy while the other will not receive therapy. If therapy decreases wound healing time, asymmetric healing/healing may occur.
- 7) Embolization and Death. This risk has been identified with Arista AH. However, this risk exists only if Arista AH is directly injected into blood vessels. In this study we will only apply Arista topically to the interior of a patient's nostril. Nothing will be injected into or applied to an open vessel. Furthermore, any excess Arista will be removed with postoperative irrigation.

There are no other additional adverse reactions to these products associated with being in this study.

5. **Describe any risks related to performing study procedures. Please include all investigational, non-investigational, and non-invasive procedures (e.g., surgery, blood draws, treadmill tests).**

**Unknown Side Effects**

There is always the risk of developing previously unknown side effects.

Patients may encounter these risks regardless of participation in this research study.

If side effects or discomforts do occur, [name] will try to minimize and treat these by irrigating the

**Protocol Title:** Analysis of hemostatic agents compared to physiologic hemostasis

---

treated sinus with saline to remove the Arista, Nexfoam, Sinufoam, Nasopore, Nexfoam, Posisep and Posisep X.

The investigator is willing to discuss any questions the participant might have about these risks and discomforts.

6. Describe any risks related to the use of radioisotopes/radiation-producing machines (e.g., X-rays, CT scans, fluoroscopy).

7. Describe why this investigational compound/drug/device/procedure's risks/benefits are potentially better than standard of care or other common alternatives. Any standard treatment that is being withheld must be disclosed and the information must be included in the consent form. **\*?HELP?\***

There is conflicting data in previous studies whether hemostatic agents are better than treatment with nothing or all. The goal is to answer that question definitively. Other options are to have both sides treated with a hemostatic, have neither side treated, or to place non-absorbable packing material that requires later removal.

8. Describe any psychological, social, or legal risks the subject may experience. **\*?HELP?\***

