**Please save frequently**

- c) Describe the study design (e.g., single/double blind, parallel, crossover, control, experimental, observational, etc.). If the study is investigator-initiated, a timeline for individual subject recruitment, follow-up, and analysis for the study is required. Also, indicate if the subjects will be randomized.

Our study is a prospective comparison between absorbable hemostatic agents as a group and the body's natural hemostatic ability without aid of therapy in patients undergoing bilateral sinus surgery with or without septoplasty.

We calculated the sample size and power analysis in the following way:

Given the number of statistical tests, we calculated a Bonferonni correction to set the alpha for the analysis at 0.017 (alpha originally at .05 divided by the number of tests = .05/30 = 0.017). Using G-Power statistical software, power analyses were completed using the Means: Wilcoxon-Mann-Whitney test (two groups). Given alpha at 0.017 and Power at 0.80, we determined that a total of 244 participants (122 in the control group, 122 in the hemostatics group) would be needed to detect a medium effect size (d=0.5). Since one nostril will be used as the control and the therapy applied to the other side, the number of participants needed drops to 122.

Based on previous studies, we conservatively expect a dropout rate of 15%. In order to maintain the same number of participants, we would need to enroll a total of 144 participants

Postoperatively, patients will rate subjective symptoms such as nasal obstruction, bleeding,

**Protocol Title:** Analysis of hemostatic agents compared to physiologic hemostasis

---

pain, and nasal discharge on a scale ranging from 1-10, of which 10 is the most severe. Similarly, the treating physicians on endoscopic examinations will rate objective measures such as mucosal edema, infection, time spent debriding, and synechiae formation. (Please see the attached patient and physician questionnaires) Patient questionnaires will be completed on postoperative days #1, 2, 7, and 14. Surgical healing outcomes will be noted during routine postoperative visits 1 and 2 weeks after surgery. Expected total duration of each subjects' participation is 6 weeks. Total subject accrual should take no longer than one year. Data analysis will take up to three months. Estimated time of completion is 03/2018.

d) **If subjects will be given placebo, please justify placebo use. \*?HELP?\***

N/A

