- c) If the proposed study is a clinical trial where a drug, vaccine, device or other treatment is compared to a placebo group or comparison treatment group, what are the guidelines or endpoints by which early decisions regarding efficacy or lack of efficacy can be made? For example, it may be reasonable to stop enrollment on a study when efficacy has already been clearly demonstrated, to avoid unnecessary enrollments of additional subjects. Alternatively, it may be reasonable to stop enrollment when it is clear that efficacy will never be demonstrated, given the statistical power of the study as designed. Describe the guidelines that are in place to assist in making these determinations, if relevant to the proposed study.

If side effects or discomforts do occur, [name] and/or [name] will try to minimize and treat these by irrigating the treated sinus with saline to remove the Arista, Nexfoam, Sinufoam, Nasopore, Posiseq, or Posiseq X.

- d) Describe how data analysis will be performed (statistical tests, methods of evaluating data) and indicate the smallest group/unit for which separate reporting will occur. For studies involving a questionnaire, if data and reliability information are available, please describe or provide references. For full board, unfunded studies describe sample size determination and power analysis. If none, please justify.

Means and standard deviations will be obtained for data collected from patients and the physician. These outcomes will be used for comparative evaluation of hemostatic agents (n=144) against no therapy. Statistics will include descriptive statistics and a non-parametric ANOVA comparing the questionnaire patient data and the physician data followed by Post-hoc multiple comparisons.

Please save frequently

- e) State if deception (including incomplete disclosure of study purpose/procedures) will be used. If so, describe the nature of the deception and provide a rationale for its use. Also, describe debriefing procedures or justify a waiver of the requirement to debrief. NOTE: for studies using deception, an alteration of consent must be justified in the Informed Consent section of the protocol (#13) and the debriefing script/statement must be uploaded in the Attachments section (#16). See IRB Deception Guidelines.

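### Section 3d plans means, SDs and tests but no within-patient difference with an interval, so a non-significant result would not show which effects it rules out

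*Combined protocol and SAP*

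**What the plan says.** Section 3b gives each patient an agent in one nostril and nothing in the other, so the comparison is within patients. Section 9 (Risks), item 7, notes conflicting earlier data on whether agents are better than nothing and adds: "The goal is to answer that question definitively".

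The analysis is set out in section 3d. "Means and standard deviations will be obtained for data collected from patients and the physician", and the inference is "descriptive statistics and a non-parametric ANOVA comparing the questionnaire patient data and the physician data", with post-hoc comparisons afterwards. Nowhere do the documents name a treated-minus-untreated estimate, a confidence interval, a smallest important difference, or a way of reading a non-significant result.

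The significance level comes from section 2c: "we calculated a Bonferonni correction to set the alpha for the analysis at 0.017". The derivation there is "alpha originally at .05 divided by the number of tests = .05/30 = 0.017". The sample size follows: "Given alpha at 0.017 and Power at 0.80, we determined that a total of 244 participants", split equally between the two arms, for d=0.5, using an unpaired Wilcoxon-Mann-Whitney calculation. This is then reduced to 122 patients because each serves as their own control, and raised to 144 for 15% dropout. Sidedness and the correlation between a patient's two sides are not stated.

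**The concern.** A paired design earns its precision from the difference between the two sides of one patient. A mean and SD for each side, with a test result, do not carry that precision: the SD of the difference also depends on the side-to-side correlation, which is neither assumed in the plan nor a planned output.

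This matters most when a test is not significant. A difference estimated tightly around zero and a sizeable difference just short of a strict threshold would both appear as non-significant. A reader deciding whether an agent is worth using would need to know which had occurred. Section 3f reports that surgeons are split about evenly on using an agent, so a null result would be read with interest.

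**Working it through.** **Inputs.** From section 2c: 122 pairs after dropout, d=0.5, power 0.80, alpha printed as 0.017 and derived as 0.05/30. Assumed here, because the documents are silent: side-to-side correlation ρ from 0 to 0.5, equal SDs on the two sides, two-sided testing. Effects are in units of the per-side SD.

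**Step 1: the plan's own figures.** 0.05/30 = 0.00167, not 0.017. The sample size was checked with a two-sample noncentral t calculation, with n multiplied by 3/π for the Wilcoxon-Mann-Whitney test under normality:

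| Alpha | One-sided, n per group | Two-sided, n per group |
|---|---|---|
| 0.017 | 75 | 89 |
| 0.00167 | 122 (power 0.801) | 136 |

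Of these, only 0.00167 one-sided reproduces 122. Dropout reproduces: 122/0.85 = 143.5, rounded up to 144. Both alphas are carried forward because the text prints one and computes the other.

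**Step 2: what the per-side SDs leave out.** With a per-side SD of 1, the SD of the paired difference is √(2(1−ρ)). A reader with only the two SDs must use √2. The ratio is √2/√(2(1−ρ)) = 1/√(1−ρ), which is 1 at ρ=0 and 1.41 at ρ=0.5. The rebuilt interval is then 41% too wide.

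**Step 3: how often a real effect is non-significant.** Paired t, n=122, noncentrality = d√122/√(2(1−ρ)). For d=0.3 this is 2.34 at ρ=0 and 3.31 at ρ=0.5. The critical t on 121 df is 2.42 at alpha 0.017 and 3.22 at 0.00167.

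| True d | Missed at 0.017 (ρ=0 to 0.5) | Missed at 0.00167 (ρ=0 to 0.5) |
|---|---|---|
| 0.3 | 53% to 19% | 80% to 46% |
| 0.4 | 24% to 2% | 53% to 12% |

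A signed-rank approximation (efficiency 3/π) gives much the same for d=0.3: 55% to 21% and 82% to 49%.

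**Step 4: what an interval would show.** The SE of the paired mean difference is √(2(1−ρ))/√122 = 0.128 at ρ=0 and 0.091 at ρ=0.5. The 95% half-width is 1.98 × SE = 0.25 or 0.18 SD. The largest non-significant estimate is critical t × SE:

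| Alpha | ρ | Largest non-significant estimate | Its 95% CI |
|---|---|---|---|
| 0.017 | 0 | 0.31 | 0.06 to 0.56 |
| 0.017 | 0.5 | 0.22 | 0.04 to 0.40 |
| 0.00167 | 0 | 0.41 | 0.16 to 0.67 |
| 0.00167 | 0.5 | 0.29 | 0.11 to 0.47 |

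Compare an estimate of zero at ρ=0.5, with 95% CI −0.18 to 0.18. All these results are non-significant. Only the paired interval separates them.

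**The case against.** The strongest reply is that this is a superiority study. Section 1a asks whether agents are superior to none and also raises possible harm through synechiae. The objectives in section 2b speak of relative efficacy, and the word definitively occurs only in a Risks answer. On that view the study owes no equivalence conclusion, and the absence of intervals is silence in a short form answer, not a decision to omit them.

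Much of this stands, and it limits what can be claimed.

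- A reader might infer that null results will be reported as no difference. The documents do not say so; they give no rule either way.
- A reader might infer that the analysis can support only the answer that agents help. A two-sided comparison could also show harm.
- A reader might infer that a null result could never be told from an inconclusive one. At a correlation of about 0.5 or more, the 95% CI of any non-significant result would exclude d=0.5. But neither the correlation nor the SD of the difference is a planned output, so a reader could not know this.
- A reader might want to use ±0.5 SD as an equivalence margin. In section 2c, d=0.5 is a generic medium effect chosen for detection, not a stated clinically important difference.

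The miss rates also depend heavily on which alpha applies. Finally, the questionnaires are attachments not available here, and the text does not say that patients rate each nostril separately. Where they do not, no within-patient difference exists.

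None of this removes the gap. A superiority study still needs an effect estimate with its precision, and section 3d names neither.

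**Conclusion.** The point holds as a gap in the analysis method and should be corrected. The outputs named in section 3d do not give the size or precision of the within-patient difference, so a non-significant result would not show which effects it excludes. A true d=0.3 would be missed in 53% to 19% of trials at 0.017 and in 80% to 46% at 0.00167. These figures rest on 122 pairs, an assumed correlation of 0 to 0.5, equal SDs, and a two-sided paired t test as a stand-in for the non-parametric analysis. The gap exists under either alpha; its size does not stay the same, so the contradiction in section 2c must be settled as well.

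The documents do not support the stronger conclusions that the plan intends to call null results equivalence, or that it must meet a fixed equivalence margin.

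**What to change.** In section 3d, for each outcome recorded separately by side:

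1. Make the within-patient treated-minus-untreated difference the basis of inference. Use the Hodges-Lehmann median difference for scores and the paired difference in proportions for binary outcomes.
2. Report each with a 95% CI and a multiplicity-adjusted CI at the corrected alpha, after reconciling 0.017 with 0.05/30 in section 2c.
3. State that non-significance alone will not be read as no difference, and that null results will be described by the effects their CI excludes.

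No fixed ±0.5 SD equivalence rule should be added. The Expedited Paragraphs section, item 8(c), marks the remaining activity as data analysis. If data have already been seen, the change should be dated and labelled as made after that point.

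The cost is a few sentences and slightly more analysis work, with no extra patients or visits. The downside is that some null outcomes will have to be reported as inconclusive.
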